9.3.3 Assay description including Site Performing Correlative Study

The purpose of this study is to confirm on-target effects. Samples will be thawed on ice then up to 3 ml of plasma or 5 ml of urine will be processed. Cell-free nucleic acids will be extracted using the QIAamp circulating Nucleic Acid kit (Qiagen). Samples will be eluted in 20-30 ul of elution buffer and then quantified with Picogreen assay. A ddPCR (droplet digital PCR) duplex assay will be run on 5 ul of each extraction using the QX-100 system from BioRad. The conditions of the different assays have already been optimized to detect both wild-type (HEX probe) or mutant (FAM probe). Results will be analyzed using QuantaSoft software.

9.4 Neuroimaging Studies

Patients will have MRI Brain with and without contrast with diffusion performed prior to therapy, every 2 courses for the first 6 courses, and after every 3 courses thereafter, until time of progression or completion of treatment. MRI Spine should be performed prior to therapy and at the same time points as standard MRI Brain, if clinically indicated. The MR parameters will be listed on the PBTC NIC web page under MR protocols. Only scans showing a response, the confirmation scan obtained approximately 8 weeks later if available, and the corresponding baseline scan will be uploaded for central review.

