Patients will be followed initially for the resolution of all toxicities considered at least possibly related to panobinostat occurring while on treatment and for 30 days after the last administration of study drug. Patients will continue to be followed for 3 years from the initiation of protocol treatment for the monitoring of unexpected later developing toxicities or other morbidity and to document disease progression and survival. Once patients are off-treatment and treatment-related toxicities have resolved or another treatment started, follow up during this 3-year period may be done electronically or by phone. Data should be updated quarterly in the PBTC Rave database.

5.3.4 *Criteria for Removal from Study*

The date and reason for the patient coming off study must be documented in the eCRF and the OBDMC must be notified according to standard reporting guidelines (see Sections 7 for adverse events, Section 5.3.5 for Data submission for Off Study, Section 12 for Data Reporting, and the Required Data and Timetable Submission from located on the PBTC-047 protocol webpage).

- Patient determined to be ineligible.
- Parent, patient, or guardian withdraws consent for continued participation.
- Patient death while on study. The IRB, Study Chair and OBDMC must be notified as per Section 7.3.
- Patients removed from treatment for reasons other than withdrawal of consent or Death will be followed until three years have elapsed from the date of initiation of protocol therapy on this study.

5.3.5 *Data Submission for Patients Off-Study*

No data will be collected documenting treatment or reporting events or disease status that occur subsequent to the official “off study” date, with the exception of adverse events with an attribution of possible, probable, or definite that occur after the “off study” date for agents being studied under an IND (see **Section 7**).

6 Dosing Delays/ Dose Modification

6.1 *Notification of Study Chair*

The study chair or co-chair must be notified of any dosage modifications, prior to the implementation of the dose modification

6.2 *Hematologic and Non-Hematologic Adverse Events and Management*

The criteria for dose modifications for study drug-related toxicity are detailed in **Table 13**.

Dose Modification for Hematological Toxicity

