9.4.2 Image Transfer

Standard MRI with gadolinium and diffusion images obtained at each time point, including progression during the extended follow-up period if applicable, will be electronically transferred to the PBTC Neuroimaging Center (NIC). All patient specific data are stripped from the images and replaced with PBTC Accession numbers prior to transmitting the images to the NIC. All image data transfer is accomplished using PGP (pretty-good-privacy) 128-bit encryption which meets industry standard for secure communication

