9.5 Autopsy Studies

Sites are encouraged to obtain an autopsy when possible and appropriate on enrolled patients. Performing pathologists will be requested to look for evidence and extent of immune cell infiltration in the specimen.

Specifically, it is recommended that the following assessments be made and documented in the autopsy report:

- 9.5.1 Determine areas of necrosis and attempt analysis for cause/etiology, if possible.
- 9.5.2 Determine the extent of lymphocyte infiltration particularly in adjacent areas of edema / inflammation.

In addition, 15-20 slides will be requested to perform staining for characterization of infiltrating lymphocyte population and other studies. Please ensure this is covered in your site's autopsy consent form.

10 Study Calendar

Data is to be submitted according to the Data submission timelines located on the PBTC-047 webpage.

Table 18

	Pre-therapy	Course 1	Courses 2-Course 26	Completion/Discontinuation Of Treatment	Off Tx Follow-up
Physical Assessments					
Panobinostat Administration, patients with recurrent/progressive DIPG (Stratum 1)		1 x/day, 3x/week every other day for 3 weeks. 1 week rest	1 x/day, 3x/week every other day for 3 weeks. 1 week rest		
Panobinostat Administration, patients with non-progressed DIPG or H3K27M ⁺ Thalamic DMG (Stratum 2)		1 x/day, 3x/week every other week	1 x/day, 3x/week every other week		
Medical history	X	Weekly	X	X	
Physical exam /height/weight	X	Weekly	X	X	
Vital signs	X	Weekly	X	X	
Performance status	X		X	X	
Neurologic exam	X		X	X	
Laboratory Evaluations					
CBC WBC, HgB, Platelets, ANC, ALC ^A	X	Weekly	X	X	
Serum Chemistry Sodium, Potassium, Bicarbonate, Chloride, Calcium, BUN, Creatinine, Glucose, Phosphorous, Magnesium, Albumin, Total Protein, SGPT(ALT), SGOT(AST), Total Bilirubin	X	X	X	X	
Serum or Urine pregnancy test (for females of childbearing potential)	X	X	X		
TSH, free T ₄	X			X	
Other Assessments					
EKG ^A	X	Day 1, and Day 5 (3 rd dose): Pre-dose and 3 hrs post dose	Pre-dose Day 1 of Course 2,3,4		
Echocardiogram or MUGA	X			X	
Imaging Assessments					

	Pre-therapy	Course 1	Courses 2-Course 26	Completion/Discontinuation Of Treatment	Off Tx Follow-up
Brain MRI (standard) ^B	X		After every 2 courses for the first 6 courses, then after every 3 courses until progression	End of Tx or progression	Every 3 months until progression

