Brain MRI with diffusion ^B	X		After every 2 courses for the first 6 courses, then after every 3 courses until progression	End of Tx or progression	Every 3 months until progression
Spinal MRI (if clinically indicated) ^{B,C}	X		After every 2 courses for the first 6 courses, then after every 3 courses until progression	End of Tx or progression	Every 3 months until progression

^A This should also be done whenever clinically indicated.
^B All required imaging dates are to be entered in the database. However, only scans showing a partial response or complete response, and that same subject's baseline scan, will be uploaded.
^C MRI Spine should be done at the indicated time and when clinically indicated. If no disease is present within the spine at baseline, spine MRIs will be obtained as clinically indicated and at the discretion of the primary treating physician.

Table 19

Correlative Laboratory Studies	Pre-therapy	Course 1	Course 2, 4, 6, 12
Tumor Tissue and Blood for Biorepository (optional)	X		
Pharmacokinetics Plasma (required)		
 Day 1: pre-dose and at 0.5, 1, 2, 4, 8 (± 1), and 24 (± 4) hours after the oral dose. Day 3 (2nd dose): single sample will be collected prior to the dose 	
Pharmacodynamics: Cell-free DNA – Blood (optional)		Day 1, Courses 1, 2, 4, 6, 12, prior to drug dose (Optional Biorepository: Leftover Sample Storage for Future Research)	
Pharmacodynamics: Cell-free DNA – Urine (optional)		Day 1, Courses 1, 2, 4, 6, 12, prior to drug dose, preferably in morning (No longer collected as of version 8.0)	

11 Measurement of Effect

Although the clinical benefit of panobinostat has not yet been established, the intent of offering this treatment is to provide a possible therapeutic benefit, and thus the patient will be carefully monitored for tumor response and symptom relief in addition to safety and tolerability. Patients with measurable disease will be assessed by standard criteria. For the purposes of this study, patients should be re-evaluated by MRI after every 2 courses for the first 6 courses, then every 3 courses and when clinically indicated until disease progression or off-study criteria are met.

11.1 *Definitions*

11.1.1 *Evaluable for Toxicity*

Patients who receive at least 1 dose of the study regimen and are removed from treatment for toxicity during the first course (dose-finding period) are evaluable for estimating the MTD.

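### Imaging after treatment ends is specified inconsistently, so patients who stop without progression may have no scheduled scan while PFS still runs to last follow-up

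*Combined protocol and SAP*

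**What the plan says.** Five places in the protocol bear on imaging once a patient is off treatment without progression.

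- **Section 9.4 (Neuroimaging Studies)** schedules brain MRI before therapy and then "every 2 courses for the first 6 courses, and after every 3 courses thereafter, until time of progression or completion of treatment". It gives no off-treatment interval and does not refer to the study calendar.
- **Section 10, Table 18**, in the off-treatment follow-up column, requires standard and diffusion brain MRI, and spinal MRI if indicated, "Every 3 months until progression".
- **Section 11 (Measurement of Effect)** uses the same course-based intervals as Section 9.4, "and when clinically indicated until disease progression or off-study criteria are met". Off study is not the same as off treatment: Section 5.3.4 keeps most patients on study until three years after therapy began.
- **Section 9.4.2 (Image Transfer)** describes transfer of images from each time point, "including progression during the extended follow-up period if applicable".
- **Section 5.3.3** states that "Patients will continue to be followed for 3 years from the initiation of protocol treatment", partly to document progression and survival. Once the patient is off treatment, and treatment-related toxicities have resolved or another treatment has started, "follow up during this 3-year period may be done electronically or by phone". It adds that "Data should be updated quarterly in the PBTC Rave database". It does not mention MRI.

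PFS (Sections 11.2.5 and 13.3.3) runs from the start of treatment to progression or death, and otherwise to last follow-up. Progression (Section 11.2.4) is clinical worsening, more than 25% growth in the bi-dimensional measurement, or a new lesion.

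**The concern.** PFS is a secondary objective in both strata (Sections 1.2.1 and 1.4.1). Two of the three routes to progression, growth and a new lesion, need a scan. If sites differ on whether scans continue after treatment, progression is ascertained in different ways among patients who stop without it. Where no scans are done, progression is recorded only at clinical decline or death, or the patient is censored as progression-free at the last contact.

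Such patients are foreseeable. Section 5.3.2 lists unacceptable toxicity, refusal of further treatment, non-compliance and completion of treatment as reasons to go off treatment. Section 6.2 removes a patient who has a dose-limiting toxicity after a dose reduction. Section 6.3 removes a patient who cannot be dosed for more than 7 days because of QTcF prolongation.

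**Working it through.** The plan states no figure on this point. The check is a comparison of the passages, schedule arithmetic, and an illustration on assumed inputs.

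**1. The passages side by side, for a patient off treatment without progression**

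| Place | Scheduled MRI after treatment |
|---|---|
| Section 9.4 | None given; course-based schedule only |
| Table 18 | Every 3 months until progression |
| Section 11 | Continues to progression or off study, but only course-based intervals are given |
| Section 9.4.2 | Images of progression in extended follow-up expected, if applicable |
| Section 5.3.3 | Not mentioned; phone or electronic contact allowed under conditions |

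The direct conflict is Section 9.4 against Table 18 and Section 11. Section 9.4 is the outlier. Section 5.3.3 does not forbid scans, but it gives a site a basis for omitting them. No order of precedence is stated.

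**2. How many scans depend on the reading**

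Inputs: 28-day courses (Tables 1 and 2), follow-up of 3 years from treatment start (Section 5.3.3), 3-month interval (Table 18).

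Follow-up is 3 × 365.25 = 1,095.75 days. Three months is 3 × 365.25/12 = 91.31 days. Scans due under Table 18 = whole part of (1,095.75 − 28 × courses given) / 91.31.

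| Stops after course | Day | Days left | Days left / 91.31 | Table 18 scans | Section 9.4 scans |
|---|---|---|---|---|---|
| 2 | 56 | 1,039.75 | 11.39 | 11 | 0 |
| 6 | 168 | 927.75 | 10.16 | 10 | 0 |
| 12 | 336 | 759.75 | 8.32 | 8 | 0 |
| 26 | 728 | 367.75 | 4.03 | 4 | 0 |

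These are maxima, for a patient who stays progression-free and on study.

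**3. What else could detect progression**

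In Table 18 the physical and neurologic examinations have no entry in the off-treatment column. MRI is the only disease assessment scheduled there. Under Section 9.4 combined with Section 5.3.3, nothing scheduled remains except contact.

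**4. What the censoring rule adds**

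Suppose a patient has a last scan at treatment stop and quarterly phone contacts afterwards, with no clinical decline reported. Under Sections 11.2.5 and 13.3.3 the censoring date is the last contact. Each quarterly update can therefore add about 3 months of progression-free time that no scan supports.

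**5. Illustration of size (assumed inputs, none from the documents)**

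- *Affected patients only.* Assume an exponential residual time to radiographic progression with a median of 3 to 9 months, and a mean lag from radiographic to clinical progression of 1 to 3 months. Without scans, progression is then recorded on average 0.3 to 1.9 months later than with 3-monthly scans.
- *Whole stratum.* Assume a true median PFS of 4, 6 or 8 months; 10%, 20% or 30% of patients assigned a stop at months 1 to 4, which takes effect only if they have not yet progressed; a mean clinical lag of 1 or 2 months; and no off-treatment scans at all in the comparison case. Mean PFS restricted to 12 months rises by 0.01 to 0.13 month across the 18 combinations. This covers late detection only, not the censoring effect in step 4.

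**The case against.** The strongest reply is that only Section 9.4 is out of step, and only on one reading. It gives a course-based schedule and can be taken to describe the treatment period alone. Its end point is completion of treatment, and Section 5.3.2 lists completion separately from toxicity and refusal, so read literally it does not end imaging for a patient who discontinues. Section 5.3.3 is headed as a data submission schedule, is permissive and conditional, and does not waive calendar procedures. Its quarterly updates fit the 3-monthly scans in Table 18. Clinical worsening alone counts as progression, and death is an event. PFS is descriptive, with no test or comparator.

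Most of this stands, and it limits the point. A site could follow Table 18 and breach nothing, so the conflict creates a possibility of uneven assessment and does not show that scans will be missed. It does not remove the point. Section 9.4 is the dedicated imaging section and does not say it covers treatment only. A course count also gives no further scan dates once courses end, whether by completion or discontinuation. Clinical progression is a weak safeguard when no off-treatment examination is scheduled.

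A reader might infer that PFS is inflated more at dose levels with more toxicity stops. The documents do not support that as a bias in any planned result: Section 13.3.3 analyses efficacy by stratum, and no comparison of PFS between dose levels is planned.

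**Conclusion.** The inconsistency is real and is in the current text. Patients who stop without progression may have no scheduled radiographic assessment, depending on which passage a site follows, and censoring at last follow-up lets remote contact extend PFS without a scan. The likely direction is upward.

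The size is unknown. The documents give neither the share of patients who stop without progression nor the lag between radiographic and clinical progression, and site practice cannot be known from them. It is probably small: only these patients are affected, clinical decline and death still count, and the illustrative shift in 12-month restricted mean PFS was at most 0.13 month even with every off-treatment scan omitted. That illustration rests wholly on the assumed inputs and leaves out the censoring effect.

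A reader might want to state the bias as a shift in median PFS. That would not be reliable. With scans at fixed dates, a simulated median can sit on a scan date (for example 9 × 28 = 252 days, or 8.28 months) and then jump, so the apparent shift depends heavily on the scenario chosen.

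Dose-limiting toxicities are counted in course 1, so MTD estimation is unaffected. This should be corrected, but it does not threaten the primary objectives.

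**What to change.** Reconcile the passages in line with Table 18:

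- **Section 9.4:** after the course-based schedule, add *and, for patients off treatment without progression, every 3 months until progression (Table 18)*.
- **Section 11:** refer to the same off-treatment interval.
- **Section 5.3.3:** state that phone or electronic contact does not replace the Table 18 MRI before progression. Say explicitly how patients who start another treatment before progression are handled, both for imaging and for PFS. The present text allows remote follow-up for them, so this needs a deliberate decision.
- **Sections 11.2.5 and 13.3.3:** censor PFS at the last adequate disease assessment, with that term defined, and not at the last contact. Aligning the imaging text alone would leave this gap open.

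The cost is wording in five sections and one decision on patients who start another treatment. Table 18 already requires the scans, so no procedure is added for a site that follows it. A site that has followed Section 9.4 alone would do more imaging. The censoring change needs the date of the last disease assessment, and the Table 18 footnote already has required imaging dates entered in the database.

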9.4.1 Imaging Guidelines

9.4.1.1 Brain MR with and without gadolinium will be obtained preferably on the 3T magnet consisting of:

- Sagittal T1 MPRAGE (slice thickness 1.0, 25 cm FOV)
- Axial T2 images (slice thickness 2mm skip 0, 20 cm FOV)
- Axial T2 FLAIR images (slice thickness 4mm skip 0, 20 cm FOV)
- Axial DTI images (slice thickness 2.0 mm skip 0, 22 cm FOV); 35 directions, b-values: 0 and 1000 s/mm²
- Post gadolinium sagittal T1 SPACE (slice thickness 0.9 mm skip 0, 22 cm FOV)
- Axial T1 post gadolinium images through the whole brain (slice thickness 4mm skip 0, 20 cm FOV)

9.4.1.2 Brain MR with and without gadolinium on 1.5 T:

- Sagittal T1 (slice thickness 5 mm skip 1 mm, 22 cm FOV)
- Axial T2 images (slice thickness 4 mm skip 0 mm, 20 cm FOV)

- Axial T2 FLAIR images (slice thickness 5 mm skip 0 mm, 20 cm FOV)
- Axial DWI, 6 directions (slice thickness 5 mm skip 0 mm, 26 cm FOV)
- Post gadolinium sagittal 3DFSPGR images (slice thickness 1.5 mm no skip, 24 cm FOV)
- Axial T1 post gadolinium (slice thickness 3 mm no skip, 16 cm

9.4.1.3 Protocol for Spine

- Sagittal T1 images should be after gadolinium (slice thickness 3 mm skip 0).
- Axial T1 images are after gadolinium (slice thickness 3mm skip 0). Axial T2 images are optional

9.4.2 Image Transfer

Standard MRI with gadolinium and diffusion images obtained at each time point, including progression during the extended follow-up period if applicable, will be electronically transferred to the PBTC Neuroimaging Center (NIC). All patient specific data are stripped from the images and replaced with PBTC Accession numbers prior to transmitting the images to the NIC. All image data transfer is accomplished using PGP (pretty-good-privacy) 128-bit encryption which meets industry standard for secure communication

9.4.3 Neuroimaging Review

Local review of MR imaging studies at each site and central review of the MR imaging studies will be conducted through the PBTC Neuroimaging Center (NIC). The NIC will review the imaging studies at study completion.

NIC review will include assessment of response to therapy (as feasible). All patients with a documented PR/CR at any time point will have central review of the scan showing response, the confirmation scan obtained approximately 8 weeks later, as well as the corresponding baseline scan conducted for confirmation.

9.5 Autopsy Studies

Sites are encouraged to obtain an autopsy when possible and appropriate on enrolled patients. Performing pathologists will be requested to look for evidence and extent of immune cell infiltration in the specimen.

Specifically, it is recommended that the following assessments be made and documented in the autopsy report:

- 9.5.1 Determine areas of necrosis and attempt analysis for cause/etiology, if possible.
- 9.5.2 Determine the extent of lymphocyte infiltration particularly in adjacent areas of edema / inflammation.

In addition, 15-20 slides will be requested to perform staining for characterization of infiltrating lymphocyte population and other studies. Please ensure this is covered in your site's autopsy consent form.

10 Study Calendar

Data is to be submitted according to the Data submission timelines located on the PBTC-047 webpage.

Table 18

	Pre-therapy	Course 1	Courses 2-Course 26	Completion/Discontinuation Of Treatment	Off Tx Follow-up
Physical Assessments					
Panobinostat Administration, patients with recurrent/progressive DIPG (Stratum 1)		1 x/day, 3x/week every other day for 3 weeks. 1 week rest	1 x/day, 3x/week every other day for 3 weeks. 1 week rest		
Panobinostat Administration, patients with non-progressed DIPG or H3K27M ⁺ Thalamic DMG (Stratum 2)		1 x/day, 3x/week every other week	1 x/day, 3x/week every other week		
Medical history	X	Weekly	X	X	
Physical exam /height/weight	X	Weekly	X	X	
Vital signs	X	Weekly	X	X	
Performance status	X		X	X	
Neurologic exam	X		X	X	
Laboratory Evaluations					
CBC WBC, HgB, Platelets, ANC, ALC ^A	X	Weekly	X	X	
Serum Chemistry Sodium, Potassium, Bicarbonate, Chloride, Calcium, BUN, Creatinine, Glucose, Phosphorous, Magnesium, Albumin, Total Protein, SGPT(ALT), SGOT(AST), Total Bilirubin	X	X	X	X	
Serum or Urine pregnancy test (for females of childbearing potential)	X	X	X		
TSH, free T ₄	X			X	
Other Assessments					
EKG ^A	X	Day 1, and Day 5 (3 rd dose): Pre-dose and 3 hrs post dose	Pre-dose Day 1 of Course 2,3,4		
Echocardiogram or MUGA	X			X	
Imaging Assessments					

	Pre-therapy	Course 1	Courses 2-Course 26	Completion/Discontinuation Of Treatment	Off Tx Follow-up
Brain MRI (standard) ^B	X		After every 2 courses for the first 6 courses, then after every 3 courses until progression	End of Tx or progression	Every 3 months until progression
Brain MRI with diffusion ^B	X		After every 2 courses for the first 6 courses, then after every 3 courses until progression	End of Tx or progression	Every 3 months until progression
Spinal MRI (if clinically indicated) ^{B,C}	X		After every 2 courses for the first 6 courses, then after every 3 courses until progression	End of Tx or progression	Every 3 months until progression

^A This should also be done whenever clinically indicated.
^B All required imaging dates are to be entered in the database. However, only scans showing a partial response or complete response, and that same subject's baseline scan, will be uploaded.
^C MRI Spine should be done at the indicated time and when clinically indicated. If no disease is present within the spine at baseline, spine MRIs will be obtained as clinically indicated and at the discretion of the primary treating physician.

Table 19

Correlative Laboratory Studies	Pre-therapy	Course 1	Course 2, 4, 6, 12
Tumor Tissue and Blood for Biorepository (optional)	X		
Pharmacokinetics Plasma (required)		
 Day 1: pre-dose and at 0.5, 1, 2, 4, 8 (± 1), and 24 (± 4) hours after the oral dose. Day 3 (2nd dose): single sample will be collected prior to the dose 	
Pharmacodynamics: Cell-free DNA – Blood (optional)		Day 1, Courses 1, 2, 4, 6, 12, prior to drug dose (Optional Biorepository: Leftover Sample Storage for Future Research)	
Pharmacodynamics: Cell-free DNA – Urine (optional)		Day 1, Courses 1, 2, 4, 6, 12, prior to drug dose, preferably in morning (No longer collected as of version 8.0)	

11 Measurement of Effect

Although the clinical benefit of panobinostat has not yet been established, the intent of offering this treatment is to provide a possible therapeutic benefit, and thus the patient will be carefully monitored for tumor response and symptom relief in addition to safety and tolerability. Patients with measurable disease will be assessed by standard criteria. For the purposes of this study, patients should be re-evaluated by MRI after every 2 courses for the first 6 courses, then every 3 courses and when clinically indicated until disease progression or off-study criteria are met.

11.1 *Definitions*

11.1.1 *Evaluable for Toxicity*

Patients who receive at least 1 dose of the study regimen and are removed from treatment for toxicity during the first course (dose-finding period) are evaluable for estimating the MTD.

Patients who receive approximately 83-85% of prescribed therapy (i.e. $\geq 8/9$ doses in stratum 1 and $\geq 5/6$ doses in stratum 2) during the dose-finding period but who progress prior to completing the course may be considered evaluable for estimating the MTD, as long as no additional anti-cancer therapy or supportive care that would confound the interpretation of any observed toxicity or side effect is given. Patients must have completed all of the clinical and laboratory monitoring requirements specified by the protocol up to the time of disease progression for them to be considered evaluable for MTD estimation.

Patients who receive less than 83-85% of the protocol specified therapy (i.e. miss >1 dose) and who go off treatment for reasons other than toxicity (e.g., progressive disease, withdrawal of consent etc.) during the dose finding period will be considered inevaluable for estimating the MTD and may be replaced.

Patients who complete all therapy during the dose-finding period but who fail to comply with all the specified clinical and laboratory monitoring requirements for the first course may be considered inevaluable for estimating the MTD and may be replaced.

11.1.2 *Evaluable for Radiographic Response*

Only those patients who have measurable disease present at baseline, have received at least one course of therapy, and have had their disease re-evaluated will be considered evaluable for response. These patients will have their response classified according to the definitions stated below. (Note: Patients who exhibit objective disease progression prior to the first scheduled MRI will also be considered evaluable.)

